1.4. Estimand for Primary Efficacy Endpoint

The combination of treatment policy and hypothetical strategy will be used for the primary efficacy endpoint to account for the intercurrent events. The four attributes of the estimand are defined as follows:

- A. Population:** The patients with fibromyalgia met all inclusion criteria and met none of the exclusion criteria.

Statistical Analysis Plan

The modified intent-to-treat (mITT) analysis set defined in Section 3.2 will be the primary analysis set for efficacy. In the data analyses, the treatment will be assigned based on the treatment to which patients were randomized, regardless of which treatment they actually received.

B. Variable: Change from baseline to week 12 in the weekly average of the daily average PI-NRS score over the past 24 hours.

C. Intercurrent events: Treatment discontinuation due to an adverse event, due to lack of efficacy, or due to other reasons.

For those who discontinue the treatment before week 12, no further efficacy data will be collected. The use of rescue medication for fibromyalgia pain will not be considered as an intercurrent event.

D. Population-level summary: The primary efficacy endpoint, the change from baseline to week 12 in the PI-NRS scores, will be analyzed using a Mixed Model Repeated Measures (MMRM) model with change from baseline in the weekly average of the daily average PI-NRS score over the past 24 hours at weeks 1, 2, 3, 4, 5, 6, 7, 8, 9, 10, 11, and 12 as the dependent variable, sex, age group at FM onset, week, treatment, and treatment by week interaction as fixed factors, and baseline average of the daily average PI-NRS score as a covariate. An adjustment for missing data due to adverse event or due to lack of efficacy on the PI-NRS scores will be on average return to baseline values, while due to all other reasons will be imputed assuming missing at random. With missing data imputed, each of the 500 imputed data sets will be analyzed using the MMRM model. The results from the 500 analyses will be combined using Rubin’s formulae. The least square (LS) mean estimates for the mean change from baseline to each time point, as well as the difference of the estimates between the fremanezumab and placebo group, with the corresponding standard error (SE), p-value and associated 95% confidence interval (CI) will be provided.

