6.2.2. Primary Efficacy Analysis

The primary efficacy endpoint will be analyzed using a MMRM model with change from baseline in the average of the daily average PI-NRS score over the past 24 hours at weeks 1, 2, 3, 4, 5, 6, 7, 8, 9, 10, 11, and 12 as the dependent variable, sex, age group at FM onset, week, treatment, and treatment by week interaction as fixed factors, and baseline average of the daily average PI-NRS score as a covariate. The heterogeneous autoregressive correlation structure [ARH (1)] for repeated observations within patients will be used, and the denominator degrees of freedom will be estimated using Kenward-Roger’s approximation. An adjustment for missing data due to lack of efficacy or adverse events assumes the PI-NRS scores will be on average return to baseline values. Missing data (due to early treatment discontinuation or missing e-dairy recording in an entire analysis week) will be imputed 500 times to generate 500 complete data sets using the SAS procedure PROC MI following the 3 steps below.

Notes, if ARH(1) does not converge, then simpler covariance structures with less parameters will be used in the following order until the model converges: autoregressive (1) (AR[1]); heterogeneous compound symmetry (CSH); and compound symmetry (CS).

Step 1: The monotone missing pattern will be induced by the Markov Chain Monte Carlo method in the PROC MI procedure using seed number 4751523.

The average of the daily average PI-NRS score up to and including week 12 will be imputed by using following SAS code to impute the arbitrary missing data and to make the missing data pattern monotonic:

```
PROC MI DATA=name NIMPUTE= 500 SEED=4751523 OUT= MI_MONOTONE;  
  BY TRT01PN AGEATFMONST SEX;  
  MCMC IMPUTE= MONOTONE;  
  VAR BASE WEEK1 ... WEEK12;  
RUN;
```

Where TRT01PN denotes the planned treatment group; AGEATFMONST denotes the age group at FM onset; BASE denotes the baseline average of the daily average PI-NRS score; WEEK1, . . . , WEEK12 denote the weekly average of the daily average PI-NRS score in weeks. In bold are the SAS key words.

Statistical Analysis Plan

Step 2: Once the arbitrary missing data are imputed, the following SAS code will be used to impute the monotone missing data.

The remaining missing data at subsequent weeks will be imputed using the regression method for the monotone pattern with seed number 4751523 and adjustment for covariates including baseline value and all values at preceding weeks.

```

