PROC MI DATA= MI_MONOTONE NIMPUTE= 1 SEED= 4751523
OUT= MI_COMPLETE;
  CLASS TRT01PN AGEATFMONSET SEX;
  MONOTONE REG;
  VAR TRT01PN AGEATFMONSET SEX BASE WEEK1 ... WEEK12;
RUN;
```

MI_COMPLETE will be transposed to a new data set (WEEKPI0) with each week as a row.

Step 3: Use by-week mean change from baseline to adjust those who discontinued treatment due to lack of efficacy (LOE) or adverse event (AE) before week 12.

The initially missing and now imputed data for patients who discontinued from the study drug due to LOE or AE will be center adjusted at the mean baseline value. That is, the final imputed score will be equal to the imputed score under missing at random minus the observed mean change from baseline score at the post baseline time point.

```
DATA WEEKPI;
  SET WEEKPI0;
  CHANGEi = AVALi - BASE;
  IF DTREAS IN ('LACK OF EFFICACY', 'ADVERSE EVENT') AND IMP= 1
  THEN DO;
    CHANGEi = CHANGEi - MWEEK_CHG;
  END;
RUN;
```

Where AVALi denotes the value of the post baseline weekly average of the daily average PI-NRS after missing data imputation; CHANGEi denotes the change from baseline after missing data imputation; MWEEK_CHG denotes the change from baseline calculated without missing data imputation; DTREAS denotes the reason for treatment discontinuation.

Step 4: Each of the 500 imputed data sets described above steps will be analyzed using the MMRM. SAS code is:

```
ODS OUTPUT LSMEANS= LS DIFFS = DIFF (WHERE = (week = _week));
PROC MIXED DATA= WEEKPI (WHERE= (WEEK>= 1));
  BY _IMPUTATION_;
  CLASS SUBJID TRT01PN WEEK AGEATFMONSET SEX;
  MODEL CHANGEi= BASE TRT01PN AGEATFMONSET SEX WEEK
    TRT01PN*WEEK/DDFM=KR;
  REPEATED WEEK/SUBJECT= SUBJID TYPE= ARH(1);
  LSMEANS TRT01PN*WEEK / DIFF CL;
RUN;
ODS OUTPUT CLOSE;
```

Statistical Analysis Plan

Where `_IMPUTATION_` denotes the numbering of imputations; `SUBJID` denotes the subject ID; `WEEK` denotes the analysis week (12 levels: weeks 1 to 12).

Step 5: The results from the 500 analyses from Step 4 will be combined using Rubin’s formulae (`PROC MIANALYZE`). The least square (LS) mean estimates for the mean change from baseline to each time point, as well as the difference of the estimates between the fremanezumab and placebo group, with the corresponding SE, p-value and associated 95% CI will be provided.

(a) For LS means

```
PROC SORT DATA= LS;  
  BY WEEK TRT01PN _IMPUTATION_ ;  
RUN;  
  
ODS OUTPUT PARAMETERESTIMATES= LSM_O;  
PROC MIANALYZE DATA= LS;  
  BY WEEK TRT01PN;  

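### SAP Step 3 centres lack-of-efficacy and adverse-event stoppers on the observed patients' mean change, so it does not deliver the stated average return to baseline; it also names no treatment group

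*SAP*

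**What the plan says.** SAP 1.4 lists the intercurrent events as "Treatment discontinuation due to an adverse event, due to lack of efficacy, or due to other reasons". For scores missing because of an adverse event or "due to lack of efficacy on the PI-NRS scores will be on average return to baseline values"; other missing data are imputed as missing at random (MAR). SAP 6.2.2 repeats that the adjustment "assumes the PI-NRS scores will be on average return to baseline values". SAP 1.4 adds: "For those who discontinue the treatment before week 12, no further efficacy data will be collected".

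The method in SAP 6.2.2 runs as follows.

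- Step 2 imputes the remaining missing weeks by regression with "adjustment for covariates including baseline value and all values at preceding weeks".
- The Step 3 heading begins "Use by-week mean change from baseline to adjust those who discontinued treatment due to lack of efficacy" and goes on to include AE stops. The final value is the "imputed score under missing at random minus the observed mean change from baseline score at the post baseline time point".
- The code note says "MWEEK_CHG denotes the change from baseline calculated without missing data imputation". Neither text nor code gives this mean a treatment index.

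Protocol 9.6.4.1 and the protocol synopsis describe the same subtraction but take the mean change within the patient's treatment group. They do not say whether that mean is observed or imputed; the word observed is the SAP's. The SAP Introduction says that the SAP is meant to agree with the protocol but prevails where they differ. SAP section 18 lists no changes.

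**The concern.** The stated target and the stated operation do not match. Centring a group on zero change requires subtracting that group's own mean. Step 3 subtracts the mean of other patients, those still observed at that week. Patients who stop for lack of efficacy have, if the label means anything, improved less than those who stay, and Step 2 carries their poor weeks forward. Subtracting the stayers' larger improvement puts them above baseline.

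No efficacy data are collected after a stop before week 12, so Steps 2 and 3 together determine what these patients contribute afterwards. The primary objective is to estimate the treatment effect, and Step 5 reports the arm means as well as the differences. No planned analysis would reveal the mismatch: the sensitivity analysis in SAP 6.2.3 alters only rescue-day scores and then reuses 6.2.2, and the worst-pain and responder analyses inherit the same imputation.

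The missing treatment index is a separate gap. If a programmer took the mean over all arms, the adjustment would act differently on the contrast.

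**Working it through.** **1. The design figure, for scale.** Inputs from SAP 2.4: SD 2.2, 80 per arm, 95% CI, half length below 0.74 with probability at least 90%.

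Half length = t(0.975, 158) × s × √(2/80), with s² distributed as 2.2² × χ²(158)/158. This gives P(half length < 0.74) = 0.918 at n = 80 and 0.897 at n = 79, so the plan's statement is reproduced. The expected half length is about 1.975 × 2.2 × 0.158 = 0.69. At 51 per arm (153/3, the number randomized at Amendment 05; the final number is not given) it is 1.984 × 2.2 × √(2/51) = 0.86.

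**2. Algebra of Step 3.** For one arm and week, let p be the fraction stopped for LOE or AE, d their mean MAR-imputed change, and o the observed mean change.

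- Mean final change of the stoppers = d − o. The target is 0, met only if d = o.
- Shift in the arm mean = p(d − o).
- Error in the contrast = p(d − o) in active minus p(d − o) in placebo.
- With a mean m pooled over arms and equal p, the contrast becomes MAR contrast − pm + pm, which is the MAR contrast.

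**3. One worked case (simulation).** Assumed: true week-12 means −1.5 placebo and −2.0 active, SD 2.2, week-to-week correlation 0.9, LOE stopping dependent on pain, 4000 per arm, 15 repeats.

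| | Placebo | Active |
|---|---|---|
| LOE / AE fraction | 0.11 / 0.05 | 0.09 / 0.05 |
| Observed mean o | −1.64 | −2.12 |
| MAR mean, LOE / AE | −0.45 / −1.56 | −0.94 / −2.14 |
| Final change, LOE / AE | +1.19 / +0.08 | +1.17 / −0.02 |
| Final change, LOE and AE together | +0.84 | +0.74 |

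By arm, the contrast error is 0.14 × 0.74 − 0.16 × 0.84 = 0.104 − 0.134 = −0.03. The simulated contrasts agree: −0.467 as written by arm against −0.438 at exact return to baseline. The placebo mean is −1.236 instead of −1.372. A pooled mean gives −0.541, and plain MAR −0.508.

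Over the variants in which LOE depended on pain, LOE stoppers landed at +0.82 to +2.17. When it did not, they landed at 0.00 to +0.06.

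**4. Wider range (large-sample limit, 60,000 per arm).** Assumed: the same means; SD rising from 1.2 to 2.2; AR(1) 0.8 or 0.95, exchangeable 0.5 or 0.7, or 0.5 + 0.5 × 0.8^lag; LOE odds ratio per point 1.16, 1.35 or 2.2; 0% or 5% response-unrelated AE stops. LOE stoppers land at +0.2 to +2.1, AE stoppers at −0.05 to +0.15.

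| LOE placebo / active | Error in week-12 difference, by-arm means |
|---|---|
| 10% / 10% | about 0.01 or less |
| 10% / 5% | 0.01 to 0.10 toward the drug |
| 15% / 5% | 0.02 to 0.20 toward the drug |
| 5% / 10% | 0.01 to 0.09 against the drug |
| 5% / 15% | 0.02 to 0.19 against the drug |

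The largest value is 0.20/0.69 = 29% of the half length at 80 per arm, or 0.20/0.86 = 23% at 51.

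**5. Trial-size check.** 400 trials, 80 per arm, exchangeable 0.7, 5% AE, regression imputation with parameter draws, 20 imputations. As written by arm against target:

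| LOE placebo / active | Odds ratio 1.35 | Odds ratio 2.2 |
|---|---|---|
| 10% / 10% | −0.44 vs −0.44 | −0.44 vs −0.44 |
| 15% / 5% | −0.62 vs −0.55 | −0.65 vs −0.47 |
| 5% / 15% | −0.25 vs −0.33 | −0.22 vs −0.41 |

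The pooled reading at 10%/10% LOE plus 5% AE gives −0.51, the MAR value, against −0.44.

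**The case against.** The best defence is that Step 3 is a coherent prespecified rule with a loose description: it removes the average improvement and keeps each patient's own deviation. That is a fair account of what the formula does. But SAP 1.4 and 6.2.2 apply the return to baseline to the data missing for LOE or AE, not to an average patient. If the sponsor prefers the existing rule, those two sentences must be reworded; as they stand, target and formula disagree.

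It can also be said that the effect on the contrast is small, in a proof-of-concept study already stopped for futility. This largely stands. With by-arm means and equal LOE stopping the error is negligible, and the upper values need a threefold imbalance with steep selection.

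Four stronger readings are tempting and not supported:

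- **That the SAP prescribes a pooled mean.** It states no such rule. It intends agreement with the protocol, lists no changes, and carries the treatment variable in Steps 1, 2 and 4. This is an omission, worth closing because the SAP prevails.
- **That the error favours the drug.** It favours whichever arm has fewer LOE stops.
- **That LOE and AE must each centre on baseline.** SAP 1.4 names the events separately but sets one joint target.
- **That the futility decision was affected.** The interim methods are in separate plans that are not available here.

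**Conclusion.** The point holds and should be fixed. Step 3 does not in general return LOE and AE stoppers to baseline on average. LOE stoppers land about +0.2 to +2 points too high if LOE stopping depends on pain, and about right if it does not; AE stops unrelated to response land near baseline. With by-arm means the consequence is mainly in the arm-level means. The contrast changes materially only if LOE stopping is unequal between arms.

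The direction for LOE stoppers rests on their having improved less than those still observed, which is very likely but not quantified in the documents. All sizes rest on assumed dropout, correlation and selection. The algebra does not. The missing treatment index is a drafting gap whose consequence arises only if a pooled mean is actually programmed. Restoring it alone does not cure the centring problem, because the protocol does not centre on the discontinuers either.

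**What to change.** 1. Restore the treatment-group restriction in the Step 3 text and define MWEEK_CHG by treatment group and week.
2. To meet the stated target, replace the observed mean in MWEEK_CHG with the mean MAR-imputed change of the LOE/AE discontinuers themselves, by treatment group and week, averaged over the 500 imputations. Separate means for LOE and AE are optional: either way the group averages 0 in each arm, so the week-12 contrast is the same. If values are instead imputed directly around baseline, state that the draws have mean change 0 and do not condition on post-baseline weeks before the stop. Conditional draws still leave LOE stoppers at about +0.2 to +1.8; in the trial-size check, direct imputation put LOE and AE stoppers within 0.03 of 0 and the contrast within 0.002 of target.
3. Apply the adjustment only to weeks after the treatment stop; the present code condition does not say so. Set AVALi = BASE + CHANGEi, because the code changes only CHANGEi while the responder formula in SAP 6.3.3 uses the post-baseline value.
4. Record the change in SAP section 18.

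Cost: a few lines of text and code before database lock, and no new data. The drawback is noise in the centring mean when few patients stop for LOE or AE in an arm. With separate means at 80 per arm, 14% to 22% of arm-by-reason groups had two or fewer patients. Precision of the contrast did not suffer: its SD was 0.34 to 0.36 with direct imputation or by-reason centring, against 0.34 to 0.38 as written.

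### SAP 6.2.2 Step 3 returns every imputed week of a lack-of-efficacy or adverse-event stopper to baseline, whenever the week or the stop fell, against its own heading and the SAP 1.4 estimand

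*SAP*

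**What the plan says.** Four statements in the SAP bear on which imputed weeks go back to baseline.

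- **What is imputed (6.2.2).** "Missing data (due to early treatment discontinuation or missing e-dairy recording in an entire analysis week) will be imputed 500 times". A wholly missed diary week can therefore occur while the patient is still on treatment.
- **What the estimand shifts (1.4).** The return-to-baseline rule is "An adjustment for missing data due to adverse event or due to lack of efficacy on the PI-NRS scores"; data missing for any other cause follow the second half of the sentence, "while due to all other reasons will be imputed assuming missing at random".
- **Step 3 heading (6.2.2).** The step is there to "adjust those who discontinued treatment due to lack of efficacy (LOE) or adverse event (AE) before week 12".
- **Step 3 sentence and code (6.2.2).** The sentence reads "The initially missing and now imputed data for patients who discontinued from the study drug due to LOE or AE will be center adjusted", and the code condition is "IF DTREAS IN ('LACK OF EFFICACY', 'ADVERSE EVENT') AND IMP= 1". On the variables, the SAP says "DTREAS denotes the reason for treatment discontinuation", which is a patient-level item with no timing. IMP is used but not defined.

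Protocol 9.6.4.1 Step 3 is as broad as the SAP's Step 3 sentence. The SAP introduction says the SAP takes precedence where the two differ.

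**The concern.** The estimand and the heading tie the shift to data missing because of a discontinuation for lack of efficacy (LOE) or an adverse event (AE), and the heading adds that this happened before week 12. The code and the sentence tie it only to the kind of patient. Two sorts of value are then shifted that should stay as imputed under missing at random (MAR):

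- a week missed by a patient who stopped for LOE or AE only after week 12. If that week is week 12, the primary time point is affected directly;
- a diary week missed on treatment by a patient who later stopped for LOE or AE.

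In either case a diary lapse is scored as loss of benefit because of a later event. Two programmers working from the heading, the sentence and the code could also produce different primary results. The same steps serve the rescue-medication sensitivity analysis (6.2.3), the 30% and 50% responder analyses (6.3.3, if they use the shifted values) and worst pain (6.3.4). The sensitivity analysis carries the same condition and so cannot reveal the problem.

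**Working it through.** **1. Three illustrative patients against the texts**

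| Patient | Code and sentence | Heading | Estimand (1.4) |
|---|---|---|---|
| No diary gaps; stops for LOE in week 9, nothing recorded afterwards | Missing weeks to 12 shifted | Shifted | Shifted |
| Week 3 wholly missed, weeks 4 to 8 recorded, stops for AE in week 9 | Week 3 shifted as well | Patient included; silent on week 3 | Week 3 MAR |
| Weeks 1 to 11 recorded, week 12 wholly missed, dose 4 given, stops for LOE in week 14 | Week 12 shifted | Patient excluded | Week 12 MAR |

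That the week-3 gap is on treatment follows from SAP 1.4: "For those who discontinue the treatment before week 12, no further efficacy data will be collected". A missing week followed by a recorded one therefore precedes the stop. For the third patient, SAP Table 2 sets week 12 as the seven days before the fourth dosing day, so a patient who received dose 4 was still on treatment through week 12. Late stops are possible because treatment runs to Visit 7 (day 113).

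**2. Yardstick: the plan's own precision figure (SAP 2.4)**

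Inputs: SD 2.2, 80 per group, half length below 0.74 with at least 90% probability.

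- Expected half length = t(0.975; 158) × 2.2 × √(2/80) = 0.687.
- 90th percentile = 0.687 × √(χ²₁₅₈(0.90)/158) = 0.736.
- P(half length < 0.74) = 0.918.

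The stated figure reproduces.

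**3. Direct effect on an arm's week-12 mean**

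Wrong shift = q × |mean change|, where q is the share of the arm that stopped for LOE or AE after week 12 and has no week-12 entries. The documents give neither quantity. Assume q from 1.25% (1 of 80) to 5%, and a mean change of 1 to 2 points.

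- Low: 0.0125 × 1 = 0.0125 points (0.0125/0.74 = 1.7% of the half length).
- High: 0.05 × 2 = 0.10 points (0.10/0.74 = 13.5%).

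Per affected patient, at an assumed mean change of 1.5: 1.5/80 = 0.019. If the 153 patients randomized by Amendment 05 split equally (153/3 = 51), it is 1.5/51 = 0.029. The final arm sizes are not in the documents.

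**4. Effect on the week-12 treatment difference**

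A small simulation compared the code as written with a shift of off-treatment weeks only. It used two arms of 80, 12 weekly values, serial correlation 0.85, SD rising from 1.2 to 2.2, a treatment-by-week model with a baseline slope, the mean change taken by arm, and 150 data sets per scenario. Mean improvement at week 12 was 2.0 against 1.5 points (2.5 against 1.5 in the last row). All rates are assumed and equal in the two arms.

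| LOE/AE stops (share after week 12) | On-treatment weeks wholly missed | Patient-weeks wrongly / rightly shifted | Mean move | SD of move | Largest move |
|---|---|---|---|---|---|
| 10% (30%) | 5% | 7 / 60 | 0.002 | 0.011 | 0.03 |
| 15% (40%) | 10% | 22 / 83 | 0.004 | 0.021 | 0.06 |
| 20% (50%) | 20% | 60 / 87 | 0.013 | 0.045 | 0.13 |

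The average moves are 0.002/0.74 = 0.3% to 0.013/0.74 = 1.8% of the half length. The SD of the move exceeds its mean in every row, so the sign varies from data set to data set. Wrong shifts confined to weeks 1 to 11 moved the week-12 difference by at most 0.0024: the imputed data are complete and the model has a treatment-by-week term, so little carries over to week 12.

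**The case against.** **IMP is undefined and may carry the timing.** Step 1 fills intermittent gaps and Step 2 fills the remaining tail. If IMP marked only Step 2 values, the week-3 gap would not be shifted. That is possible, but the Step 3 sentence points to all initially missing values. The narrower reading would also leave the late-stop problem: the imputation ends at week 12, so a missing week 12 after eleven recorded weeks is a tail value, filled in Step 2.

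**The heading already excludes late stoppers.** It does, and a reader should not infer that the sponsor planned to score them as failures. The documents support a mismatch between the heading and the code beneath it. The mismatch still has to be resolved, because the code is what would be run.

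**The trigger is rare.** One diary entry makes a week non-missing (SAP 6.1.3). The protocol provides next-morning make-up reports, daily central review of diary data and weekly 75% compliance checks. Missing all of week 12, then receiving dose 4, then stopping for LOE or AE should be uncommon. This stands, and it limits the size.

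**The protocol wording is equally broad.** True for on-treatment gaps, so that conflict is between Step 3 as a whole and the estimand. For late stops, the code conflicts with its own heading too.

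**A cut at the discontinuation date would misclassify.** With injections 28 days apart, that date could mean the last dose, the decision or the termination visit. A patient who abandons the diary because treatment is failing may be recorded as an LOE stop only later. This is a fair objection to a bare date rule, and the fix below avoids it.

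**Conclusion.** The point holds as a specification error with a small expected effect. On its plain reading, Step 3 shifts imputed weeks that the heading excludes (stops after week 12) or that the estimand leaves as MAR (weeks missed on treatment). This rests on IMP meaning any imputed weekly value, which the adjacent sentence favours but the SAP does not state.

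The week-12 contrast would probably move by about 0.002 to 0.013 points on average, against a half length of 0.74. The largest single-data-set move, 0.13, came from the deliberately heavy scenario. These figures depend on assumed stop rates, missed-diary rates and mean changes. Earlier-week estimates are affected more directly.

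A reader might infer a systematic bias toward no effect. The documents do not support that for the treatment difference. Within an arm that improves on average, each wrong shift reduces that arm's apparent improvement, but the difference moves according to which arm has more affected patients. Extra shifts in the placebo arm would enlarge the apparent benefit. Nor do the documents show that the primary result would change materially, since they give no count of wholly missed weeks or late stops.

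**What to change.** Amend SAP 6.2.2 Step 3 in four places:

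1. Define IMP.
2. Add to the condition that discontinuation for LOE or AE occurred before the end of analysis week 12. This also settles whether a stop during week 12 counts, which the heading leaves open.
3. Limit the shift to the terminal block of missing weeks belonging to that discontinuation, meaning the weeks after the last observed diary week. Gaps followed by recorded data stay MAR, as do all imputed weeks of patients who stopped later.
4. Reword the Step 3 sentence to match.

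The terminal-block rule needs no choice among dose, decision and visit dates to decide which weeks are shifted, and it captures patients who stop recording shortly before a recorded LOE stop. It will also shift an ordinary diary lapse that happens to run into such a stop; the SAP should state that choice.

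The cost is a few lines of programming and one SAP sentence, which every analysis reusing Steps 1 to 3 would inherit. SAP 2.5.2 provides for amendments approved before database lock.

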6.2. Primary Efficacy Endpoint and Analysis

6.2.1. Definition

The primary efficacy endpoint is the change from baseline to week 12 in the weekly average of the daily average PI-NRS score over the past 24 hours.

Baseline is defined as the last 14 days before the first dose of IMP (Visit 3). The analysis weeks for post-baseline will be derived using rule described in [Table 2](#).

The baseline and post baseline weekly average of the daily average PI-NRS pain scores over the past 24 hours will be derived using formula [1], respectively.

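### The primary MMRM fits one baseline slope for all 12 weeks; if the slope steepens with time, week 12 is under-adjusted for baseline, at a small cost in precision that one model term removes

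*SAP*

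**What the plan says.** SAP 6.2.1 sets the target: "The primary efficacy endpoint is the change from baseline to week 12 in the weekly average of the daily average PI-NRS score". SAP 6.2.2 then fits all 12 weekly change scores together, with "baseline average of the daily average PI-NRS score as a covariate". In the Step 4 code the model statement reads "MODEL CHANGEi= BASE TRT01PN AGEATFMONSET SEX WEEK" and ends with "TRT01PN*WEEK/DDFM=KR", so treatment is the only term allowed to vary by week. The covariance line is "REPEATED WEEK/SUBJECT= SUBJID TYPE= ARH(1"), and WEEK "denotes the analysis week (12 levels: weeks 1 to 12"). If ARH(1) fails, "simpler covariance structures with less parameters will be used in the following order until the model converges": AR(1), then CSH, then CS.

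Protocol 9.6.4.1 has the same fixed effects and the same covariance structure. Neither document contains a baseline-by-week term. The sensitivity analysis in SAP 6.2.3 replaces scores on rescue-medication days and refits the same model, so it does not relax the common slope. By contrast, the Step 2 imputation regresses each week on baseline and all preceding weeks, so there the role of baseline may differ from week to week.

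**The concern.** The relation between baseline pain and change in pain need not be the same at week 1 and week 12. A later score is commonly less correlated with baseline than an early one, which makes the slope of change on baseline steeper (more negative) with time. A single BASE coefficient cannot follow this. It becomes a weighted average of the 12 weekly slopes, and the weights come from the covariance model, not from the week of interest.

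At stake is how much the covariate does at week 12: it should reduce the residual variance and correct chance baseline differences between arms. The study's primary objective is to estimate the treatment effect and its sample size rests on confidence-interval width, so precision at week 12 is the relevant currency.

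**Working it through.** **1. The plan's own precision figure.** SAP 2.4 gives n = 80 per group, SD 2.2 for change, and at least 90% probability of a 95% CI half-length below 0.74. Half-length = t(0.975, 158) × s × √(2/80). At s = 2.2 this is 1.975 × 2.2 × 0.1581 = 0.687. The bound of 0.74 corresponds to s = 0.74 / (1.975 × 0.1581) = 2.370, and P[χ²(158) < 158 × (2.370/2.2)²] = 0.918. The stated 90% reproduces, and it takes no credit for a baseline covariate.

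**2. What the common slope estimates.** With complete (imputed) data and a saturated treatment-by-week term, and ignoring sex and age group, the week-12 estimate is D12 − b × D0. D12 is the arm difference in mean week-12 change and D0 the arm difference in mean baseline. The slope is b = Σ w_t β_t, with weights w = V⁻¹1 / (1′V⁻¹1), where β_t is the true slope at week t and V the ARH(1) covariance. If all β_t are equal, b equals that value and nothing is lost, whatever V is.

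**3. The weights.** SDs and correlations are assumptions. The SD moves linearly to 2.1 at week 12; in the last column the true slope runs linearly from −0.10 to −0.50.

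| SD at week 1 | lag-1 correlation | week-1 weight | week-12 weight | common slope |
|---|---|---|---|---|
| 1.0 | 0.80 | 0.60 | 0.08 | −0.19 |
| 1.0 | 0.90 | 0.93 | 0.06 | −0.14 |
| 1.0 | 0.93 | 1.13 | 0.04 | −0.10 |
| 1.4 | 0.80 to 0.93 | 0.42 to 0.77 | 0.13 to 0.15 | −0.24 to −0.17 |
| 2.1 (flat) | 0.90 | 0.33 | 0.33 | −0.30 |

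Week 12 needs −0.50. Under-adjustment occurs in every row because the slope steepens; the concentration on early weeks also needs a rising SD. A week-1 weight above 1 is offset by negative weights later, so the common slope can even be shallower than every weekly slope.

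**4. Cost at week 12.** The variance per patient is residual variance + SD₀² × (β12 − b)², where SD₀ is the baseline SD. Take a strong but plausible case scaled to the plan's SD of 2.2: SD₀ = 1.4, β12 = −0.57, b = −0.04.
- Week-specific slope: 4.84 − 1.96 × 0.57² = 4.20; SE = √(4.20 × 2/80) = 0.324.
- As written: 4.20 + 1.96 × 0.53² = 4.75; SE = 0.344 from unrounded slopes.
- No baseline term: 4.84; SE = 0.348.

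The SE as written is 0.344/0.324 − 1 = 6.2% larger than with the fix; the CI half-lengths are 0.680 and 0.640.

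**5. Range.** SAP 2.1 limits mean baseline pain to 4 to 9, and a uniform spread on that range has SD 1.44. Over 60 assumed scenarios (baseline SD 1.0 to 1.44, SD of change rising to 2.2, baseline-to-week-12 correlation 0.26 to 0.64):
- Weeks 1 to 3 together carry 0.61 to 0.99 of the weight; week 12 carries 0.01 to 0.12.
- The SE penalty is 0% to 6.7%, median 0.5%. The maximum equals losing 1 − 1/1.067² = 12% of the patients.
- In the 20 scenarios with a week-12 slope of −0.2 or steeper, the common slope is a median 21% of the week-12 slope, and the median SE penalty is 1.6%.

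Direct fits to simulated trials (3 × 80, 300 replicates) agree: common slopes of −0.043, −0.229 and −0.105 against week-12 slopes of −0.574, −0.554 and −0.321. A separate simulation (65 per arm, baseline SD 1.25) gave SE penalties of 0.4%, 1.6% and 3.5% with steepening slopes. It gave none with a constant slope or with a slope moving only from −0.05 to −0.15.

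**6. Chance imbalance.** In the case of step 4, a baseline difference of 0.3 points leaves 0.3 × 0.53 = 0.16 points uncorrected. A one-SE baseline difference there is 1.4 × √(2/80) = 0.22, which leaves 0.12.

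**The case against.** The common-slope model is not an error: protocol and SAP agree on it, and it is a legitimate estimator. Subtracting baseline in the outcome already does much of the work. Randomization keeps the contrast unbiased on average, and ARH(1) estimates the week-12 SD freely, so the reported SE reflects the poorer fit. The planned precision does not depend on the covariate: even in the strong case the half-length is 0.680, below 0.74. Every weekly SD, slope and correlation above is assumed. The trial is an estimation-focused proof of concept, already stopped for futility (SAP 2.5.1 and 2.5.2), and an SE change that is usually under 2% is unlikely to alter its reading.

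Nearly all of this stands, and it fixes the size of the point. It does not remove the point, because the restriction serves no stated purpose and no planned analysis tests it.

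A reader might infer more: that baseline adjustment is lost altogether, that the week-12 result is biased, or that type I error is inflated. The documents do not support these readings. In the strong case the SE as written (0.344) is close to that of the plain change score (0.348), but a plain change score is itself baseline-subtracted. Null rejection rates in the three simulated settings were 5.7%, 6.3% and 8.0%, with a Monte Carlo SE of √(0.05 × 0.95/300) = 1.3 points. In the run with 8.0%, even the contrast without the covariate had an empirical SE of 0.360 against 0.348 expected. Runs of this size neither show inflation nor exclude a small departure.

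**Conclusion.** The point holds as a cheap improvement to precision, not as a flaw in validity. One slope is imposed on 12 weeks, and it under-adjusts at week 12 if the true slope steepens. The shortfall is larger if the SD of change also rises, because ARH(1) then takes the slope mainly from the first weeks. With a flat SD, the first and last weeks weigh equally. The fallback structures differ too: CS weights all weeks equally, AR(1) weights the two ends equally, and CSH is again early-weighted when the SD rises.

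The week-12 SE is 0% to about 7% larger than with week-specific slopes, usually under 2%, and there is no loss under a constant slope. These sizes rest on assumptions that the documents neither confirm nor contradict. That the SE stays valid rests on the free week-12 SD and on ARH(1) describing the residual correlation adequately.

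**What to change.** Add BASE*WEEK to the Step 4 MODEL statement in SAP 6.2.2, with the matching words in the model description there and in the estimand (SAP 1.4). Carry it into the daily worst PI-NRS analysis in SAP 6.3.4, which reuses that model. Week 12 then gets its own baseline slope. The change can be made by SAP amendment before database lock, which SAP 2.5.2 allows for while the randomization codes are still blinded.

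The cost is 12 slopes in place of 1, so 11 more fixed-effect parameters. LS means are already evaluated at the mean baseline by default and need no change.

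The same term may be added to the FIQR and PROMIS models for consistency, but no gain has been calculated there. FIQR, Physical Function and Fatigue use only weeks 4, 8 and 12, so the early-week weights above do not carry over to them.
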